### 9.1.2. Management of Elevated Transaminase Levels (ALT and/or AST)

Nearly all instances of elevated transaminases due to bardoxolone methyl treatment are expected to be asymptomatic. Check transaminase levels (as well as TBL, GGT, alkaline phosphatase (ALP), and International Normalized Ratio (INR)) within 48 to 72 hours during an unscheduled visit if the following occurs:

ALT or AST levels > 5X ULN

Repeat testing every 72 to 96 hours until transaminase levels are below 5X the ULN for at least one week or until the patient withdraws consent.

Discontinue study drug administration permanently if any of the following occurs:

- ALT or AST > 8X ULN
- ALT or AST > 5X ULN for more than 2 weeks
- ALT or AST > 3X ULN and (TBL > 2X ULN or INR > 1.5)
- ALT or AST > 3X ULN with the appearance of fatigue, nausea, vomiting, right upper quadrant pain or tenderness, fever, rash, and/or eosinophilia (> 5%)

The hepatobiliary tree must be visualized (e.g., ultrasound, magnetic resonance imaging [MRI]) and assessed if a patient discontinues taking study drug secondary to elevated transaminase levels. Additional tests/studies may be warranted depending on the clinical presentation.

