#### 8.5.1. Patient Discontinuation Criteria

Discontinuation refers to a patient's stopping administration of study drug. Reasons for study drug discontinuation may include the following:

- Occurrence of an AE or change in medical status that leads the investigator to be concerned about the patient's welfare
- Administrative reasons (e.g., inability to continue)
- Sponsor termination of the study
- Voluntary withdrawal
- Females who become pregnant during the study

Patients must discontinue study drug if any of the following occur.

- ALT or AST > 8X ULN;
- ALT or AST > 5X ULN for more than two weeks;
- ALT or AST > 3X ULN and (total bilirubin > 2X ULN or INR > 1.5);
- ALT or AST > 3X ULN with the appearance of fatigue, nausea, vomiting, right upper quadrant pain or tenderness, fever, rash, and/or eosinophilia (> 5%).

Patients who are discontinued from study drug should still continue in the study, complete all study visits, and undergo all scheduled study assessments, if possible.

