# 9.10.20. Clinical Chemistry

Samples will be collected for the following clinical chemistry analyses as indicated in Table 5: ferritin, creatine kinase (CK), BUN, enzymatic creatinine, eGFR, TBL, direct bilirubin, ALT, AST, ALP, sodium, potassium, calcium, phosphorus, uric acid, total protein, glucose, albumin,

lactate dehydrogenase (LDH), magnesium, chloride, bicarbonate, and GGT. Women of childbearing potential will require a serum pregnancy test (hCG-Qual) at the Screen A visit or at any point in time if a pregnancy is suspected.

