# 9.10.23. Hematology

Samples will be collected for the following hematology assessments as indicated in Table 5: hematocrit, hemoglobin, hemoglobin A1c, red blood cell (RBC) count, white blood cell (WBC) count, neutrophils, bands (if detected), lymphocytes, monocytes, basophils (if detected), eosinophils (if detected), absolute platelet count, mean corpuscular hemoglobin (MCH), mean corpuscular volume (MCV), and mean corpuscular hemoglobin concentration (MCHC).

[figure not shown]

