		\geq 18	34 U/L
	Male	< 18	40 U/L
		\geq 18	36 U/L
TBL			Central lab ULN
INR			Central lab ULN

Urinalysis results other than pH and specific gravity will not be summarized. Results not summarized include of ketones, protein, blood, glucose, clarity, color, leukocytes, nitrite,

bilirubin, and microscopic examinations (if indicated based on laboratory results), urine microscopic findings, and pregnancy test results will not be summarized.

Laboratory results that are above or below normal limits will be flagged in the listings.

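### An INR above 1.5 is a mandatory stop once ALT or AST exceeds 3X ULN, but INR is required only in a recheck triggered above 5X ULN, and SAP Table 7 counts a different INR threshold

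*Protocol*

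**What the plan says.** **Stopping rule.** Protocol 8.5.1 lists as a mandatory discontinuation "ALT or AST > 3X ULN and (total bilirubin > 2X ULN or INR > 1.5", with the bracket closing after the INR value. Section 9.1.2 repeats the rule and makes the stop permanent. The INR cut is an absolute 1.5.

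**When INR is measured.** Section 9.1.2 calls for transaminases, bilirubin, GGT, ALP "and International Normalized Ratio (INR)) within 48 to 72 hours during an unscheduled visit if the following occurs". The trigger is "ALT or AST levels > 5X ULN". It continues: "Repeat testing every 72 to 96 hours until transaminase levels are below 5X the ULN for at least one week".

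**Where INR is absent.** The chemistry list in 9.10.20 ("ferritin, creatine kinase (CK), BUN, enzymatic creatinine, eGFR, TBL, direct bilirubin, ALT, AST, ALP, sodium, potassium, calcium" and so on, ending with GGT) has no INR. Nor does the hematology list in 9.10.23 ("hematocrit, hemoglobin, hemoglobin A1c, red blood cell (RBC) count, white blood cell (WBC) count, neutrophils" and further counts and indices), the schedule in Table 5, or the minimum content of an unscheduled visit in 9.7.

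**What the SAP counts.** The combined row of SAP Table 7 (section 12.2) uses INR above 1.5 times ULN. Table 8 defines the ULN for INR as "Central lab ULN" and gives no number. Section 12.2 describes the Table 7 counts as covering any time in the study. SAP section 7 keeps unscheduled and repeat measurements out of summary tables unless otherwise specified.

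**The concern.** A mandatory stop should come with the test that decides it. Here one limb applies from 3X ULN, while the required test starts only above 5X. For patients between those levels, whether the INR limb is evaluated depends on whether a site happens to order the test. The patient who could be missed has INR above 1.5, bilirubin at or below 2X ULN, none of the listed symptoms and no eosinophilia.

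The SAP row adds a second problem. Several Table 7 rows follow the protocol's hepatic stopping rules, so a reader will take the combined row as the count of patients who met that rule. With a different INR cut it is not. No planned summary shows how many patients above 3X had an INR at all, so a low count could reflect absent tests. Safety after 12 weeks is a primary objective in every cohort.

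**Working it through.** The plan states no figure that depends on this point, so there is nothing to reproduce. The check sets the rules side by side; the arithmetic only gives scale.

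**Step 1: is an INR required where the rule applies?**

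| Patient's ALT or AST | INR limb applies? | INR required? |
|---|---|---|
| At or below 3X ULN | No | No |
| Above 3X, never above 5X | Yes | No |
| Above 5X | Yes | Yes, within 48 to 72 hours, then every 72 to 96 hours |
| Fallen below 5X, within the following week | Yes, if above 3X | Yes, reading the repeat testing as the panel just listed |
| Still above 3X after that week | Yes | No |

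The gap is rows two and five. Section 9.7 permits visits for additional tests, 9.1.2 says further tests may be warranted, and 11.6 requires follow-up of drug-related abnormal results. None of these requires an INR.

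**Step 2: how many patients?** Inputs: 4% to 11% above 3X ULN in earlier studies (protocol 5.1.2.2); about 25 patients per cohort and 100 in total (7.2). Expected count = n x p.

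- All cohorts: 100 x 0.04 = 4; 100 x 0.11 = 11.
- One cohort: 25 x 0.04 = 1; 25 x 0.11 = 2.75.
- Probability of at least one in a cohort, 1 - (1 - p)^25: 0.64 at 4%, 0.95 at 11%.

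The share who exceed 3X but never 5X is not given. Assumed values:

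| Assumed share | Low (of 4) | High (of 11) |
|---|---|---|
| 25% | 1 | 2.75 |
| 50% | 2 | 5.5 |
| 75% | 3 | 8.25 |

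This gives about 1 to 8 patients without a required INR. It leaves out the last row of Step 1, for which the documents give no figure. It counts absent tests, not missed stops.

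**Step 3: how far apart are the two INR cuts?** SAP cut = 1.5 x ULN; protocol cut = 1.5. The ULN is assumed.

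| Assumed INR ULN | SAP cut | INR values that meet the protocol's cut but not the SAP's |
|---|---|---|
| 1.0 | 1.50 | none |
| 1.1 | 1.65 | above 1.50 to 1.65 |
| 1.2 | 1.80 | above 1.50 to 1.80 |
| 1.3 | 1.95 | above 1.50 to 1.95 |

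A patient above 3X ULN with an INR in the last column and bilirubin at or below 2X ULN must stop under the protocol but is not counted in the combined row.

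**Step 4: would correcting the cut repair the row?** Not by itself. INR is required only at unscheduled visits, which section 7 excludes from summary tables by default. Whether the any-time wording in 12.2 overrides that default is not stated.

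**The case against.** The case for leaving the plan alone has weight. Nearly all patients on this drug have transaminase rises, expected to be asymptomatic, so a 5X trigger for extra visits is a defensible choice. Section 5.1.2.2 reports that the rises were not accompanied by bilirubin increases or other signs of liver toxicity, and that persistent values above 3X were not seen. Bilirubin is measured at every in-clinic treatment visit, eosinophils are in the hematology panel, and the symptom limb is broad. The investigator may also stop drug for any worrying event. All of this stands, and it keeps the clinical effect small. It does not supply the INR that a mandatory rule relies on.

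A reader might infer that no INR is ever required below 5X. That goes too far: on its natural reading, the repeat testing in 9.1.2 includes INR and continues until values have been below 5X for at least a week.

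Reflex INR testing might be arranged in a laboratory manual. Table 8 does anticipate central INR results, and the manual is not available to check. The protocol does not refer to it for INR, however, so the claim is limited to what the protocol requires.

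Table 7 is descriptive and changes no treatment decision. Discontinuations also appear in the disposition summary and among adverse events leading to discontinuation, and "Laboratory results that are above or below normal limits will be flagged in the listings". This limits the harm, but listings and disposition counts do not correct a row that applies another threshold.

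**Conclusion.** Both parts hold, and the point is minor. The protocol requires no INR for patients who peak above 3X but not above 5X ULN, or for those still above 3X once the recheck has ended. For them the INR limb depends on discretionary testing. Separately, the SAP's combined row departs from the protocol's rule for any central laboratory ULN other than 1.0.

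The scale is about 4 to 11 of 100 patients above 3X, of whom about 1 to 8 would have no required INR. This rests on earlier-study rates carrying over to different diseases, a titrated regimen and a 30 mg dose, and on an assumed 25% to 75% share who never pass 5X. The true figures could be lower or higher.

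A reader might infer that this many patients would wrongly stay on drug. The documents do not support that: the number with INR above 1.5, bilirubin at or below 2X ULN and no listed symptom or eosinophilia is not given and is expected to be very small. The SAP mismatch does not alter the stopping rule at sites or the primary eGFR analysis.

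**What to change.** **Protocol 9.1.2.** Require an INR within 48 to 72 hours when ALT or AST first exceeds 3X ULN, and with each later chemistry draw until both are at or below 3X. Keep the 5X trigger for repeats every 72 to 96 hours. No other test need be added, because the 9.7 minimum already includes chemistry.

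**SAP Table 7.** Change the INR cut to above 1.5. State that unscheduled INR, ALT, AST and bilirubin results count toward the any-time rows despite the section 7 default. Beside the combined row, show how many patients above 3X ULN had an INR.

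**Cost.** With 4 to 11 patients above 3X and an assumed 1 to 3 draws each, about 4 x 1 = 4 to 11 x 3 = 33 INR samples, some of which the existing recheck already covers. Extra unscheduled visits number about 1 to 8 under the assumed shares, since patients above 5X already return for the recheck. Later INRs go with chemistry draws that are taking place anyway. The SAP changes add no patient burden.

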# 9.1.3. Management of Muscle Spasms

Basic symptomatic relief is the first step in managing muscle spasm, including walking, adequate hydration, wearing socks, and stretching before bedtime. Assessment of levels of electrolytes such as magnesium, calcium and potassium may indicate the need for replacement. If vitamin D levels are low, supplementation may be warranted. Muscle relaxants may also help relieve symptoms.

### 9.1.4. Weight Loss

Ongoing assessments to ensure that the patient is receiving adequate nutrition and consideration of other etiologies of weight loss may be warranted for patients receiving bardoxolone methyl.

### 9.1.5. Hypomagnesaemia

In instances where a patient experiences hypomagnesaemia, defined as serum magnesium less than 1.3 mEq/L (0.65 mmol/L), consideration should be given to repletion of serum magnesium.

# 9.1.6. Management of Urinary Protein

Although increases in urinary protein with bardoxolone methyl have not been associated with renal injury or loss of kidney function, investigators should closely monitor patients if urinary albumin to creatinine ratios increase by more than 100% and exceed 1000 mg/g for proteinuria associated with nephrotic syndrome. Other concurrent signs of nephrotic syndrome include serum albumin levels below 3.5 g/dL, peripheral edema, increased blood pressure, increased BNP, or other signs of fluid retention. If nephrotic syndrome is suspected, the medical monitor should be consulted to discuss appropriate measures, which may include dose adjustment, temporary study drug discontinuation, and/or administration of loop diuretics.

# 9.1.7. Management of Blood Pressure

Investigators should attempt to maintain the blood pressure within the range recommended by the Kidney Disease Blood Pressure Working Group (KDIGO):  $\leq$  140 mm Hg systolic and  $\leq$  90 mm Hg diastolic for patients with UACR < 30 mg/g, and  $\leq$  130 mm Hg systolic and  $\leq$  80 mmHg diastolic for patients with UACR > 30 mg/g (KDIGO, 2012). Patients should receive the maximally tolerated labeled daily dose (MTLDD) of an ACE inhibitor and/or ARB, which is defined as the dose at or below the labeled dose that does not exhibit any intolerable adverse effects (e.g., hypotension, hyperkalemia), based on the investigator's assessment. If the patient is currently receiving one drug (ACE inhibitor or ARB) below the maximum labeled dose, the drug should be titrated to the MTLDD based on the assessment of tolerability by the investigator at least 6 weeks prior to the Screen A visit. Diuretics may be titrated to help maintain blood pressure target levels.

Any changes in ACE inhibitor or ARB use or diuretic therapy should be preceded by consideration of any relevant contraindications as per the local product information.

### 9.1.8. Nausea

Nausea may occur with higher doses of bardoxolone methyl. Nausea AEs are typically mild and reversible within a few weeks after treatment initiation. If symptoms do not resolve, dose descalation, with consultation of the medical monitor, may be necessary.

# 9.2. Description of Study Drug

Bardoxolone methyl (RTA 402) drug product information is shown in Table 6.

Table 6: Bardoxolone Methyl Drug Product Information

Description	Bardoxolone methyl capsule (5 mg, 15 mg)
Route of Administration	Oral

### 9.3. Concomitant Medications

#### 9.3.1. Excluded Medications

Patients taking these medications or treatments will be ineligible for enrollment:

- Any other investigational drug or device as part of an interventional study;
- Chronic (> 2 weeks) immunosuppressive therapy, or need for corticosteroids, including therapies such as glucocorticoids, oncologic preparations, and anti-TNFα agents [e.g., infliximab (Remicade®), adalimumab (Humira®), certolizumab pegol (Cimzia®), etanercept (Enbrel®)]. Glucocorticoid intra-articular injections, inhaled products, topical preparations, and nasal preparations are allowed. Patients with IgAN or FSGS that are receiving prednisone at doses ≤ 10 mg/day are eligible for enrollment in the IgAN or FSGS cohort, but prednisone doses must be stable for 30 days prior to Screen A visit and should be anticipated to remain the same for the remainder of the study.

Patients who take excluded medications during the study should not discontinue study drug solely on this basis. Consultation with the medical monitor should occur prior to study drug discontinuation or withdrawing a patient from the study.

### 9.3.2. Permitted Medications

Allowed concomitant medications include the following:

- Antibiotics;
- Daily multivitamins or recommended daily supplements;
- Other medications intended to manage concurrent diseases, as authorized by the treating physician;
- Oral, implantable, or injectable contraceptives.

Patients taking medication chronically, including ACE inhibitors and ARBs, should be maintained on those same doses and dose schedules throughout the study period and should not have additions or changes made to their medications, unless medically indicated and discussed with the Medical Monitor.

# 9.4. Treatment Compliance

The investigator or his/her designated and qualified representatives will only dispense study drug to patients enrolled in the study in accordance with the protocol. The study drug must not be used for reasons other than that described in the protocol.

### 9.5. Randomization

Not applicable.

# 9.6. Blinding

Not applicable.

### 9.7. Unscheduled Visits

Unscheduled visits are allowed for the following reasons:

- Assessment of weight gain per Section 9.1.1;
- Management of an AE or SAE;
- Performance of additional laboratory tests for clinically abnormal laboratory test values or to confirm a possible pregnancy;
- Dose re-escalation;
- Dose de-escalation;
- Any time the investigator feels that it is clinically appropriate for patient safety.

At a minimum, unscheduled visits should include collection of AEs, clinical chemistry, hematology, concomitant medications and vital signs, as well as collection/review of weight diary. Additional conversations may be necessary with the medical monitor following an unscheduled visit to assess patient safety.

# 9.8. Pregnancy

# 9.8.1. Women of Childbearing Potential

Women of childbearing potential (WOCBP) are those who are not surgically sterile (no history of bilateral tubal ligation, hysterectomy, or bilateral salpingo-oophorectomy) do not have fallopian inserts with confirmed blockage, have not had reproductive potential terminated by radiation, and are not postmenopausal for at least 1 year.

#### 9.8.2. Methods of Birth Control

During Screening, while taking study drug and until 30 days following administration of the final dose of study medication, WOCBP must practice one of the following acceptable methods of birth control:

- Use double barrier contraception method defined as male use of a condom and female
  use of a barrier method (e.g., contraceptive sponge, spermicidal jelly or cream,
  diaphragm [always use with spermicidal jelly/cream]);
- Use of hormonal contraceptives (oral, parenteral, vaginal, or transdermal) for at least 90 days prior to start of study drug administration;
- Use of an intrauterine device;
- Abstain from sexual intercourse completely. Complete abstinence from sexual intercourse is only acceptable if it is the preferred and usual lifestyle of the individual. Periodic abstinence is not permitted.

During Screening, while taking study drug and until 30 days after the final dose of study medication is taken, males who have female partners of childbearing potential must practice one of the following methods of birth control:

Have had a vasectomy (at least 6 months earlier);

Protocol 402-C-1702

- Use double barrier contraception method, defined as male use of a condom and female use of a barrier method (e.g., contraceptive sponge, spermicidal jelly or cream, diaphragm [always use with spermicidal jelly/cream]);
- Partner use of an intrauterine device;
- Partner use of hormonal contraceptives (oral, parenteral, vaginal or transdermal) for at least 90 days prior to start of study drug administration;
- Abstain from sexual intercourse completely. Complete abstinence from sexual intercourse is only acceptable if it is the preferred and usual lifestyle of the individual. Periodic abstinence is not permitted.

### 9.8.3. Suspected Pregnancy

During the study, all WOCBP must be instructed to contact the investigator immediately if they suspect they might be pregnant (e.g., late or missed menstrual period). Male patients must be instructed to contact the investigator if a sexual partner suspects she may be pregnant.

If a patient or investigator suspects that the patient may be pregnant, the study drug must be withheld until the results of a serum pregnancy test are available. If the serum pregnancy test confirms the pregnancy, the patient must permanently discontinue taking study drug. The investigator must immediately report to the medical monitor a pregnancy associated with study drug exposure. The early discontinuation protocol-required procedures outlined for End-of-treatment and Follow-up visits must be performed on the patient.

Pregnancy is not considered an AE; however, the investigator must follow a pregnant patient, or the pregnant female partner of a male patient (if consenting), and report follow-up information regarding the course of the pregnancy, including perinatal and neonatal outcome. Infants resulting from such pregnancies should be followed for a minimum of 8 weeks. Reata or designee may contact the investigator to request additional information throughout the course of the pregnancy.

The following pregnancy outcomes must be considered SAEs and will require additional reporting in the eCRF and reported as a serious AE:

- Congenital anomaly/birth defect;
- Stillbirth;
- Spontaneous miscarriage.

### 9.9. Serious Toxicities

In the case of serious toxicities, the investigator may choose to interrupt treatment with bardoxolone methyl. Dose reductions are permitted to manage tolerability issues. Patients who resume therapy after an interruption will follow the originally planned study schedule.

# 9.10. Study Procedures

The following sections describe each assessment. The timing of these assessments is noted in Table 5. All Day 1 procedures, except AE assessments, should be completed prior to administration of first dose of study drug.

### 9.10.1. Informed Consent

Written informed consent (see Section 15.3) must be obtained from the patient before any study-related procedures are performed, and again if there is a change in the study procedures that would affect the patient's willingness to participate.

# 9.10.2. Inclusion/Exclusion

Inclusion and exclusion criteria must be reviewed as indicated in Table 5. Patients must meet all of the inclusion and none of the exclusion criteria for entry in the study. Investigators should contact the medical monitor with any questions regarding eligibility prior to randomizing the patient on Day 1.

### 9.10.3. Demographics and Baseline Disease Characteristics

Demographic data including sex, age, race, and ethnicity, will be collected as indicated in Table 5. Baseline disease characteristics will be collected as indicated in Table 5.

### 9.10.4. Prior and Current Concomitant Medications

The name, dose, and frequency must be recorded for all medications that the patient is taking. All allowed and excluded medications should be recorded including all prescription drugs, herbal products, vitamins, minerals, and over-the-counter medications. Trade or generic drug names should be used where possible. Concomitant medications will be reviewed as indicated in Table 5 and all changes will be recorded.

